11. HISTORY OF GLAUCOMA OR OHT

History of glaucoma or OHT [REDACTED] will be presented for the FAS, and for PP and SAF sets [REDACTED]. The following variables will be summarized by treatment group and overall:

- Treatment status (Naive patient, Previously treated patient),
- Type of previous antiglaucoma treatment (if applicable) [REDACTED]
[REDACTED]
[REDACTED]
- For each eye:

Document: ...\\Biostatistics\\Documentation\\SAP\\ T4090-201_Statistical Analysis Plan_V1.0

Author: [REDACTED] Version Number: 1.0
Version Date: 13Nov2024

Statistical Analysis Plan

- Diagnosis (Primary OAG, OHT),
- Time since diagnosis (months) [REDACTED]
[REDACTED]
- Surgical history related to glaucoma or [REDACTED]
[REDACTED] Events will be coded using the Medicinal Dictionary for
Regulatory Activities (MedDRA) Version 27.0 or higher. [REDACTED]
[REDACTED]

Listings of history of glaucoma or OHT and related surgical history will be provided for the FAS.

12. MEDICAL AND SURGICAL HISTORY AND CURRENT CONDITIONS

Medical and surgical history and current conditions data will be summarized overall and by treatment group, for the FAS, and for PP and SAF sets [REDACTED]

- Medical history and current conditions data (other than the study disease) are captured [REDACTED]
[REDACTED]
- Surgical history data (not related to the study disease) are captured [REDACTED]
[REDACTED]

Medical and surgical history and current conditions will be coded using MedDRA Version 27.0 or higher.

The following medical and surgical history and current conditions summaries, presented by SOC and PT, will be reported for this study:

- Ocular medical and surgical history and current conditions [REDACTED]
- Systemic medical and surgical history and current conditions [REDACTED]

[REDACTED]

A listing for medical and surgical history and current conditions will be presented for the FAS.

A separate listing of related procedures/surgeries during the study [REDACTED]
[REDACTED] will be provided for the FAS.

Document: ...\\Biostatistics\\Documentation\\SAP\\ T4090-201_Statistical Analysis Plan_V1.0

Author: [REDACTED]

Version Number: 1.0

Version Date: 13Nov2024

[REDACTED]

[REDACTED]

[REDACTED]

[REDACTED]

Statistical Analysis Plan

13. MEDICATIONS

Medications reported [REDACTED] will be summarized overall and by treatment group, for the FAS, and for PP and SAF sets [REDACTED]

Medications will be coded using World Health Organization-Drug Dictionary (WHO-DD) Version March 2024 or higher.

- [REDACTED]
- [REDACTED]
- [REDACTED]
- [REDACTED]
- [REDACTED]
- [REDACTED]

Medication will be presented by Anatomical Therapeutic Chemical (ATC) Level 2 and Level 4. [REDACTED]
[REDACTED] Separate summaries for prior and concomitant medications based on ocular location (Ocular vs Systemic) will be provided.

A listing for all prior and concomitant medications will be provided for the FAS. [REDACTED]

14. STUDY TREATMENT EXPOSURE

Exposure to study treatment in days will be presented by treatment group for the SAF set.

- [REDACTED]

Document: ...\\Biostatistics\\Documentation\\SAP\\ T4090-201_Statistical Analysis Plan_V1.0

Author: [REDACTED]

Version Number: 1.0

Version Date: 13Nov2024

Statistical Analysis Plan

15. STUDY TREATMENT COMPLIANCE

Compliance (%) to study treatment will be presented separately for the study eye and the contralateral eye by treatment group for the SAF set.

Listings of all data related to study treatment administration, including interruptions, missed doses and time modifications, exposure and compliance will be provided for the SAF set.

16. EFFICACY OUTCOMES

16.1. Primary Efficacy

For this study, the primary clinical question of interest is to compare the ocular hypotensive efficacy of two concentrations of T4090 ophthalmic solution with Rhopressa® ophthalmic solution in terms of lowering the mean diurnal IOP at Week 7 in the study eye (see [Section 6.6](#)).

Document: ...\\Biostatistics\\Documentation\\SAP\\ T4090-201_Statistical Analysis Plan_V1.0

Author: [REDACTED]

Version Number: 1.0

Version Date: 13Nov2024

Statistical Analysis Plan

16.1.1. Primary Efficacy Endpoint & Derivation

The primary efficacy endpoint is the change from baseline (see calculation in [Section 6.8](#)) in the mean diurnal IOP at Week 7 in the study eye.

$$\text{Mean diurnal IOP*} = (\text{IOP at 8:00 AM} + \text{IOP at 10:00 AM} + \text{IOP at 4:00 PM}) / 3$$

* If IOP value is missing at any timepoint, the mean diurnal IOP will be missing.

Document: ...\\Biostatistics\\Documentation\\SAP\\ T4090-201_Statistical Analysis Plan_V1.0

Author: [REDACTED]

Version Number: 1.0

Version Date: 13Nov2024

Statistical Analysis Plan

16.1.3. Primary Analysis of Primary Efficacy Endpoint (Primary Estimand)

Descriptive statistics for mean diurnal IOP and change from baseline at Week 7 in the study eye will be provided by treatment group on the FAS.

The primary objective of this study is to test the hypothesis (H_0) that there is no difference in change from baseline in the mean diurnal IOP at Week 7 among treatment groups. H_0 will be tested against the alternative hypothesis H_1 of at least one of the test groups is different to reference group at 0.05 alpha level.

The primary efficacy analysis, performed for the FAS, is evaluated using a restricted maximum likelihood (REML) based, mixed-effects model for repeated measures (MMRM) estimating change from baseline across post-baseline visits. The model will include the fixed, categorical effects of treatment (T4090 0.2%, T4090 0.3%, and Rhopressa®), visit (W2, W4, and W7), and treatment-by-visit interaction, as well as the fixed, continuous covariates of baseline mean diurnal IOP value and baseline value-by-visit interaction (see [Section 7.1](#)). The general form of the model will then be:

$$\text{Change} = \text{Baseline} + \text{Treatment} + \text{Visit} + \text{Treatment*Visit} + \text{Baseline*Visit}$$

Significance tests will be based on LS means and Type III sum-of-squares, using a two-sided $\alpha=0.05$ (two-sided 95% CIs). P-values for the treatment effect and the treatment-by-visit interaction will be [REDACTED]. The primary comparisons of interest will be the LS mean differences between each T4090 dose and Rhopressa® at Week 7. For the treatment difference of each T4090 concentration versus Rhopressa® and both T4090 concentrations comparison, the model estimate, standard error, two-sided 95% CIs, and p-value will be reported. Additionally, the LS mean, SE, and two-sided 95% CI for change from baseline by visit will be reported for each treatment group.

Statistical Analysis Plan

A horizontal bar chart with 12 bars of varying lengths. The bars are black and set against a white background. The lengths of the bars decrease from left to right. The first bar is the longest, followed by a short bar, then a long bar, and so on, with the last bar being the shortest.

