## 4 SELECTION OF PATIENTS

#### 4.1 NUMBER OF PATIENTS

In this study, approximately 126 patients are planned to be randomized to have 120 evaluable patients (3 groups of 40 patients; see [Section 7.5](#)).

Evaluable patients will be defined as randomized patients having received at least one dose of IMP and with at least IOP measurements at the three timepoints (8:00 AM, 10:00 AM AND 4:00 PM) for one visit after randomization.

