### 4.5 PATIENT IDENTIFICATION AND RANDOMIZATION

Randomization will occur at the Randomization visit (Visit #2 – D1) after all screening and randomization procedures have been performed and eligibility for the study confirmed. The patient who meets the eligibility criteria will be randomly assigned to a treatment group and associated to a randomization number.

The randomization code list stratified by baseline IOP at 8:00 AM in class █ is generated by the IRT providers.

Patients will be randomized on a 1:1:1 basis to T4090 0.2%, T4090 0.3% or Rhopressa, respectively. The IMP will be allocated to the patients according to randomization using an interactive response system (IRT).

The IMP number should be recorded in all patient source documents and in the e-CRF.

Randomized patient who terminates their study participation for any reason, regardless of whether IMP was taken or not, will retain their randomization number.

See [Section 5.1.4](#) for details regarding masking and code breaking.

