#### **Main Analysis of the Primary Efficacy Estimand (1)**

[figure not shown]
Change from Baseline (D1) at W2, W4, and W7 in mean diurnal IOP in the study eye will be evaluated using an MMRM. The model will include treatment, visit (W2, W4 and W7), baseline mean diurnal IOP, baseline IOP at 8:00 AM in class [REDACTED], treatment by visit interaction, and baseline mean diurnal IOP by visit interaction as fixed factors and patient ID as a random factor. [REDACTED]  
[REDACTED]

LS mean difference from baseline for each treatment group by visit and estimates of the difference at each visit will be provided, along with their respective 95% CIs.

Descriptive statistics for the mean and mean difference from baseline in mean diurnal IOP by visit on study eye will also be provided.

The primary efficacy endpoint will be primarily analyzed on the FAS.

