3. STUDY DESIGN

3.1. General Description

This is a phase II, multicenter, randomized, investigator-masked, 3-parallel groups, 7-week treatment duration in patients with OAG or OHT. Approximately 126 eligible patients (naïve or using ocular hypotensive medication) were planned to be randomized on a 1:1:1 basis to T4090 (PF Kinezodianone R HCl 0.2% or 0.3%) or Rhopressa®.

The randomization lists are generated using a validated system, which involves a pseudo-random number generator so that the resulting sequence of treatments will be both reproducible and non-predictable. Access to the codes will be controlled and documented.

Randomized patients will attend 3 visits (Visit #3 to #5) at the investigator center during the study treatment period:

- Visit #1: Screening visit,
- Visit #1.1: Optional visit planned according to the investigator's judgement,
- Visit #1.2: Visit in case of extension of the washout period,
- Visit #2 – Day 1 (D1): Randomization visit,
- Visit #3 – Week 2 (W2) - Day 15 (± 2 days),
- Visit #4 – Week 4 (W4) - Day 29 (± 3 days),
- Visit #5 – Week 7 (W7) - Day 50 (± 3 days): End of treatment visit.

At the Randomization visit (D1; Visit #2), patients will be randomly assigned, after stratification according to their baseline IOP at 8:00 AM [REDACTED] to one of the following 3 treatment arms:

Test product:

- T4090 (PF Kinezodianone R HCl 0.2%) ophthalmic solution, in single-dose container (SDC),
- T4090 (PF Kinezodianone R HCl 0.3%) ophthalmic solution, in SDC.

Reference product:

- Rhopressa® (preserved netarsudil 0.02%) ophthalmic solution, in multiple-dose container (MDC).

The patient will administer the assigned treatment (T4090 0.2% or T4090 0.3% or Rhopressa®) once daily at 8:00 PM (± 1 hour) in the conjunctival cul-de-sac of each eye from Day 1 to the day before the End of treatment visit (Week 7; Visit #5).

Document: ...\\Biostatistics\\Documentation\\SAP\\ T4090-201_Statistical Analysis Plan_V1.0

Author: [REDACTED] Version Number: 1.0

Version Date: 13Nov2024

Statistical Analysis Plan

The maximum study duration will be 12 weeks: 5-week washout period (including optional 1-week washout extension) (See Section 3.1.1 of the Protocol), and 7-week treatment period. A minimum of 4 visits and a maximum of 7 visits are planned. The number of visits will depend on the patient's screening status (naïve patient or patient using ocular hypotensive medication).

Figure A Overall design of the study (pre-treated patient)

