3.2. Sample Size

This is a Phase II pilot study, and the analysis is to be considered as exploratory. Therefore, no formal sample size calculation is performed. It is planned to randomize 126 patients with a randomization scheme 1:1:1 with a stratification by baseline IOP at 8:00 AM in class [REDACTED]

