7. STATISTICAL CONSIDERATIONS

7.1. Adjustments for Covariates and Factors to be Included in Analyses

The following covariates and factors will be used in the analyses. For details of their inclusion in the models, see the specific analysis section.

- Baseline IOP – continuous value,
- Treatment (T4090 0.2%, T4090 0.3%, and Rhopressa®),
- Visit (W2, W4, and W7).

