10. DEMOGRAPHIC AND OTHER BASELINE CHARACTERISTICS

Demographic data and other baseline characteristics will be presented by treatment group and overall for the FAS.

Document: ...\\Biostatistics\\Documentation\\SAP\\ T4090-201_Statistical Analysis Plan_V1.0

Author: [REDACTED]

Version Number: 1.0

Version Date: 13Nov2024

Statistical Analysis Plan

and for PP and SAF sets [REDACTED]. No statistical testing will be carried out for demographic or other baseline characteristics. The following demographic and other baseline characteristics will be reported for this study:

Demographics:

- Age (years) – as continuous, and in two classes: Adult (18-64), Older Adult (65+),
- Sex (Male, Female),
- Race (American Indian or Alaska Native, Asian, Black or African American, Native Hawaiian or Other Pacific Islander, White, Not Reported, Unknown),
- Ethnicity (Hispanic or Latino, Not Hispanic or Latino, Not Reported, Unknown),
- Iris color (Blue, Gray, Green, Brown, Hazel, Other),
- Baseline IOP at 8:00 am in the study eye in classes [REDACTED]

A listing of the above demographic data will be provided for the FAS. This listing will also include:

- Childbearing potential (Yes, No) and birth control method – for female only,
- Study Eye (Right, Left), as determined in [Section 6.6](#).

[REDACTED]
[REDACTED]
[REDACTED]
[REDACTED]

Baseline values of the efficacy and safety endpoints will be provided in statistical tables with assessments at W2, W4, and W7.

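### The SAP's primary MMRM omits the randomization stratification factor (8:00 AM baseline IOP class) that the protocol's primary model includes

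*SAP*

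**What the plan says.** Both documents stratify the 1:1:1 randomization by one named factor. Protocol 4.5: "The randomization code list stratified by baseline IOP at 8:00 AM in class". SAP 3.1: "patients will be randomly assigned, after stratification according to their baseline IOP at 8:00 AM". SAP 3.2 repeats it: "with a stratification by baseline IOP at 8:00 AM in class". The cut-points and the number of classes are redacted.

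The protocol carries the factor into its primary model (Section 7.4.1.1, Main Analysis of the Primary Efficacy Estimand): "The model will include treatment, visit (W2, W4 and W7), baseline mean diurnal IOP, baseline IOP at 8:00 AM in class". Treatment-by-visit and baseline-by-visit interactions complete its fixed effects.

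SAP 16.1.3 specifies treatment, visit and treatment-by-visit as categorical effects, "as well as the fixed, continuous covariates of baseline mean diurnal IOP value and baseline value-by-visit interaction". It then writes out a formula with the same five terms. The covariate list in SAP 7.1 has three entries: treatment, visit and "Baseline IOP – continuous value". Outside the design and sample-size sections, the readable SAP uses the class only descriptively, in Section 10: "Baseline IOP at 8:00 am in the study eye in classes".

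**The concern.** The estimate, standard error, confidence interval and p-value for each T4090 concentration against Rhopressa all come from this one model. If the protocol and SAP define it differently, two primary models are available once the data are unblinded, and neither document's readable text says which prevails.

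There is also a precision question. Stratification balances the arms on the class. If the class predicts response beyond the covariates in the model, leaving it out puts its variation into the residual. Standard errors are then larger than they need to be. The protocol lists both the continuous mean diurnal baseline and the class, so it did not treat one as a substitute for the other.

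**Working it through.** **1. Fixed effects compared**

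| Fixed effect | Protocol 7.4.1.1 | SAP 16.1.3 (text and formula) |
|---|---|---|
| Treatment | yes | yes |
| Visit | yes | yes |
| Treatment by visit | yes | yes |
| Baseline mean diurnal IOP | yes | yes |
| Baseline by visit | yes | yes |
| 8:00 AM IOP class | yes | **no** |

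The protocol has six terms and the SAP five. The stratification factor is the only difference.

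**2. Could redaction explain it?** Elsewhere the factor's name stays readable and only what follows it is blacked out. The SAP's model sentence, formula and three-item list in 7.1 show no gap where the term could stand.

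**3. How much of the class does the continuous baseline absorb?** SAP 16.1.1 defines mean diurnal IOP as the average of three readings, one of them at 8:00 AM. The documents give no SD, class effect or cut-points, so everything below except the sample size is assumed.

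- Per arm: Protocol 4.1 says "approximately 126 patients are planned to be randomized to have 120 evaluable patients", and 120/3 = 40, all taken to have Week 7 data.
- Residual SD 2.8 mmHg (range 2.2 to 3.5); baseline SD 2.5 at each timepoint; correlation between timepoints 0.7.
- Two equal classes, with an extra class shift *d* of 0, 1 or 2 mmHg beyond the linear effect of mean diurnal baseline.

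By hand:

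- Squared correlation of 8:00 AM IOP with mean diurnal IOP: (1 + 2 × 0.7)/3 = 0.80, so the correlation is 0.89.
- Squared correlation of a median split with its underlying normal reading: 2/π = 0.637.
- Share of class variance left after linear adjustment: 1 − 0.80 × 0.637 = 0.49.
- Added residual variance: *d*² × 0.25 × 0.49, which is about 0.12 for *d* = 1 and 0.49 for *d* = 2.
- SE ratio: √(1 + 0.12/7.84) = 1.008 and √(1 + 0.49/7.84) = 1.031. Net of about 0.2% for the extra parameter, this is roughly 0.6% and 2.9%.
- Reference SE: 2.8 × √(2/40) = 0.626 mmHg.

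**4. Simulation.** 4,000 trials per scenario, N = 120, blocks of 6 within strata, Week 7 ANCOVA on mean diurnal baseline with and without the class. Percentages were taken before rounding, so they can differ by about 0.1 from the ratio of the SEs shown.

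| Scenario | Extra shift (mmHg) | SE omitted / included | Effect of omitting |
|---|---|---|---|
| SD 2.8, 2 classes | 0 | 0.626 / 0.627 | −0.2% |
| SD 2.8, 2 classes | 1 | 0.631 / 0.628 | +0.6% |
| SD 2.8, 2 classes | 2 | 0.645 / 0.627 | +2.9% |
| SD 2.8, 3 classes | 0 | 0.625 / 0.627 | −0.3% |
| SD 2.8, 3 classes | 1 (total) | 0.629 / 0.628 | +0.1% |
| SD 2.8, 3 classes | 2 (total) | 0.635 / 0.628 | +1.2% |
| SD 2.2, 2 classes | 1 | 0.498 / 0.493 | +1.0% |
| SD 2.2, 2 classes | 2 | 0.516 / 0.493 | +4.8% |
| SD 3.5, 2 classes | 1 | 0.786 / 0.784 | +0.3% |
| SD 3.5, 2 classes | 2 | 0.798 / 0.785 | +1.7% |

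In the base case with a 2 mmHg shift, the CI half-width goes from 1.98 × 0.627 = 1.24 to 1.98 × 0.645 = 1.28 mmHg, a difference of about 0.04.

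If the extra effect is smooth instead of a step (0.25 to 0.5 mmHg per mmHg of 8:00 AM IOP, timepoint correlation 0.5 to 0.9), the change is −0.2% to +1.0%.

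Without the class, type I error was 4.4% to 5.5% and mean error stayed within 0.03 mmHg, which is Monte Carlo noise.

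**5. Second simulation.** This used N = 126, two classes, 3,000 runs per scenario, and a correlation of 0.7 to 0.9 between 8:00 AM and mean diurnal IOP. The SE ratio was 0.998 to 1.030 for class effects up to 0.6 residual SD, and reached 1.081 at 1.0 residual SD. Type I error without the class was 4.0% to 5.5%.

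**The case against.** A SAP may depart from its protocol, and SAP 3.4 exists to record departures. Only one of its entries is readable, so the removal may be declared and justified there. A supplementary model with the class could sit in redacted text after the primary model. The two clarification letters on which the SAP also rests are not available either. Dropping a categorised form of one reading in favour of a continuous average that contains it is a defensible choice. The cost is tiny for a smooth relationship, and nothing in the documents supports a 2 mmHg step. The trial is exploratory with no power target. The calculation uses a single-visit ANCOVA in place of the three-visit MMRM, and the protocol counts a patient as evaluable with complete IOP at any one post-randomization visit, not necessarily Week 7.

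Most of this stands as a limit on the size of the problem. Nothing here shows that the change went undeclared. Fewer patients at Week 7 would raise both SEs and leave their ratio almost unchanged, because the variance ratio in the hand calculation does not involve sample size. What does not stand is the inference that nothing needs doing. A declaration in SAP 3.4 would explain the difference but leave the primary model without the factor that restricted randomization, which the protocol had already specified.

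**Conclusion.** The discrepancy is real and can be checked from readable text: the SAP's primary model lacks the sole named stratification factor, and the protocol's contains it. It does not threaten validity: there is no bias and no type I error inflation. The loss is in precision and is probably small, from nil to about 1% of the SE in the milder scenarios. It is 2.9% (1.7% to 4.8% over residual SDs of 3.5 to 2.2) if a two-class factor carries an extra 2 mmHg step. These sizes rest on assumed SDs, correlations, class numbers and shifts; the mismatch itself rests on no assumption. The correction should be made because it settles which model is primary and costs almost nothing.

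**What to change.** In SAP 16.1.3, add baseline IOP class at 8:00 AM (the randomization stratum) as a fixed categorical effect, in both the model description and the formula, and add it to the list in SAP 7.1. Keep the continuous mean diurnal baseline and its interaction with visit. State whether the class is the stratum recorded at randomization or one derived from the study-eye reading, since the readable text does not say.

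The cost is one term in wording and code before unblinding, one degree of freedom per class beyond the first, and about 0.2% to 0.3% in SE if the class is not prognostic. If the removal was deliberate, giving the reason in SAP 3.4 and reporting the model with the class as a sensitivity analysis would reconcile the documents. It is the weaker remedy, because the primary model would still omit the stratification factor.

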17. SAFETY OUTCOMES

All outputs for safety outcomes will be based on the SAF set.

There will be no statistical comparisons between the treatment groups for safety data, unless otherwise specified in the relevant section.

17.1. Ocular and Systemic Adverse Events

Ocular and systemic adverse events (AEs) will be coded using MedDRA central coding dictionary, Version 27.0 or higher. Ocular and systemic AEs will be analyzed separately on the basis of the localization [REDACTED]

A TEAE is defined as an AE that occurs or worsens in severity after at least one dose of IMP has been administered.

Document: ...\\Biostatistics\\Documentation\\SAP\\ T4090-201 Statistical Analysis Plan V1.0

Author: [REDACTED]

Version Number:

1.0

Version Date:

13Nov2024

Statistical Analysis Plan

Separate descriptions of treatment-emergent ocular and systemic TEAEs will be performed by treatment group:

- Number and percentage of patients experiencing at least one TEAE, serious TEAE, study treatment related TEAE, study treatment related serious TEAE, TEAE leading to study treatment discontinuation, TEAE leading to death, TEAE by maximum severity, and treatment-emergent adverse event of special interest (AESI - only for ocular AEs),
- Number and percentage of patients experiencing at least one TEAE, as well as the number of TEAEs, by SOC and PT. The same summary table will be performed for serious TEAEs, study treatment related TEAEs, study treatment related serious TEAEs, TEAEs leading to study treatment discontinuation, and treatment-emergent AESI (only ocular),
- Number and percentage of patients experiencing at least one TEAE, by SOC, PT, and maximum severity. The same summary table will be performed for study treatment related TEAEs,
- Number and percentage of patients experiencing at least one TEAE, by SOC, PT, and maximum relationship to study treatment.

Listings will include all AEs (TEAEs and non-TEAEs)

